3. OBJECTIVES AND ENDPOINTS

	Objective	Endpoint
Pri	mary (efficacy)	
•	To demonstrate non-inferiority of daprodustat to darbepoetin alfa based on hemoglobin (Hgb)	Mean Hgb during the primary efficacy evaluation period (Weeks 40 to 52)
Pri	ncipal secondary (efficacy)	,
• Otl	To demonstrate superiority of daprodustat to darbepoetin alfa in terms of achievement/maintenance of target Hgb her secondary (efficacy, PK)	Number (%) of subjects with mean Hgb in the target range (10.0-12.0 g/dL) during the primary efficacy evaluation period (Weeks 40 to 52)
•	To evaluate the appropriateness of the starting dose of daprodustat	 Change from baseline in Hgb at Week 4 (Hgb increase rate) Number (%) of subjects by Hgb change from baseline category at Week 4
•	To evaluate dose adjustment scheme of daprodustat	 Distribution of the dose level Duration of treatment interruption due to Hgb >13 g/dL Frequency of dose adjustments
•	To evaluate the overall Hgb control of daprodustat using darbepoetin alfa as control	 Hgb and change from baseline at each assessment visit Number (%) of subjects who have a Hgb level within the target range (10.0–12.0 g/dL) at each assessment visit Time (%) in Hgb target range (10.0–12.0 g/dL) during the primary efficacy evaluation period (Weeks 40 to 52) Number (%) of subjects who have an Hgb level of less than 7.5 g/dL Number (%) of subjects who have an Hgb increase of more than 2 g/dL over any 4 weeks Number (%) of subjects who have an Hgb level of more than 13.0 g/dL and number of episodes
•	To evaluate the PK of daprodustat	AUC and Cmax of plasma daprodustat
Ex	ploratory	
•	To evaluate the effect of daprodustat on iron use using darbepoetin alfa as control	 Dose of i.v. iron during the study period and the primary efficacy evaluation period (Weeks 40 to 52) Number (%) of subjects who use i.v. iron during the study period and the primary

Objective	Endpoint
	efficacy evaluation period (Weeks 40 to 52)
To evaluate the effect of daprodustat on	Change from baseline in ferritin
iron metabolism using darbepoetin alfa control	Change from baseline in transferrin saturation (TSAT)
	Changes from baseline in hepcidin
	Change from baseline in serum iron
	• Change from baseline in total iron binding capacity (TIBC)
Patient reported outcome	
To evaluate the effect of daprodustat on	SF-36
health-related QoL (HR-QoL) using darbepoetin alfa as control	• Changes from baseline in SF-36 HR-QoL scores [Physical Component Summary (PCS),

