4.5. Rationale for Dose Levels

Starting dose and dose adjustments of daprodustat

The starting dose (4 mg) and the dose adjustment method (maintenance dose range: 1-24 mg) for daprodustat are described in Section 6.4.

The starting dose and the dose adjustment algorithm selected for Japanese HD subjects in the present study are based on the results from a review of the longitudinal model constructed using Hgb data from six Japanese or overseas Phase II studies (PHI112844, PHI116581, PHI116582, PHI113633, PHI113747, and PHI116099) as well as the results from clinical studies. The data set used in the model analyses was based on the data of daprodustat administered in a wide dose range (0-25 mg) and included a Japanese Phase II 4-week treatment study (PHI116099) and international multi-center late Phase II 24-week treatment studies (PHI113633 and PHI113747) in which subjects in Japan participated.

Starting dose

Simulations using a longitudinal model as well as clinical data for HD subjects suggested that Hgb levels observed with prior ESA therapy is maintained for 4 weeks after a switch from prior ESA to study medication, with no rapid increase greater than 2 g/dL, at the dose level of 4 mg in ESA user subjects. Covariate analyses identified baseline Hgb, body weight, and dose level of prior ESA as major factors affecting Hgb. However, Hgb was more greatly affected by inter-subject differences in drug response to daprodustat than these factors.

Taken together, 4 mg may be an appropriate starting dose of daprodustat for the majority of ESA users.

Maintenance dose range and dose adjustment algorithm

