### 2.2. Study Objective(s) and Endpoint(s)

Objectives	Endpoints
Primary Objectives	Primary Endpoints

 
To demonstrate non-inferiority of daprodustat to darbepoetin alfa based on hemoglobin (Hgb)
 
	
 
Mean Hgb during the primary efficacy evaluation period (Weeks 40 to 52)
 

Principal Secondary Objectives	Principal Secondary Endpoints

 
To demonstrate superiority of daprodustat to darbepoetin alfa in terms of achievement/maintenance of target Hgb
 
	
 
Number (%) of subjects with mean Hgb in the target range (10.0-12.0 g/dL) during the primary efficacy evaluation period (Weeks 40 to 52)
 

Secondary Objectives	Secondary Endpoints

 
To evaluate the appropriateness of the starting dose of daprodustat
 
	
 
Change from baseline on Hgb at Week 4 (Hgb increase rate)
 

Objectives	Endpoints
	
 
Number (%) of subjects by Hgb change from baseline category at Week 4
 

 
To evaluate dose adjustment scheme of daprodustat
 
	
 
Distribution of the dose level
 
Duration of treatment interruption due to Hgb >13 g/dL
 
Frequency of dose adjustments
 

 
To evaluate the overall Hgb control of daprodustat using darbepoetin alfa as control
 
	
 
Hgb and change from baseline at each assessment
 
Number (%) of subjects who have an Hgb level within the target range (10.0–12.0 g/dL) at each assessment visit
 
Time (%) in Hgb target range (10.0–12.0 g/dL) during the primary efficacy evaluation period (Weeks 40 to 52)
 
Number (%) of subjects who have an Hgb level of less than 7.5 g/dL
 
Number (%) of subjects who have an Hgb increase of more than 2 g/dL over any 4 weeks
 
Number (%) of subjects who have an Hgb level of more than 13.0 g/dL and number of episodes
 

 
To evaluate the PK of daprodustat
 
	
 
AUC and Cmax of plasma daprodustat
 

Exploratory Objectives	Exploratory Endpoints

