**NOTES :**

- T = Table, F = Figure, L = Listing, Y = Yes display generated.
- Stats Analysis = Represents TFL related to any formal statistical analyses (i.e. modelling) conducted.
- Summary = Represents TFL related to any summaries (i.e. descriptive statistics) of the observed raw data.
- Individual = Represents FL related to any displays of individual subject observed raw data.

[1] A summary will be produced for only daprodustat group

[2] <=-2, >-2 to -1, >-1 to 0, >0 to 1, >1 to 2, and >2 g/dL. In addition, within ±1 g/dL and over ±2 g/dL

[3] Not only within the target range, but also with above and below target range will be assessed.

[4] Rosendaal method will be used (See Section 15.6.3).

[5] On-therapy Hgb values observed at scheduled visits will be included in a summary. On-therapy Hgb values observed at unscheduled visits will be included if specified (See Section 7.3.2).

[6] Summaries for dose adjustment will based on HemoCue Hgb values including those of unscheduled visits.

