**7.3.2. Summary Measure**

Hgb at each assessment visit

The values will be summarized using mean, standard deviation, 95% CI, minimum, P25, median, P75, and maximum at each assessment visit by treatment group. Graphical summaries will be provided using mean and 95% CI over time. This will also be summarized by prior ESA type, prior ESA dose, and ERI subgroup.

Change from baseline at each assessment visit

The values will be summarized using mean, standard deviation, 95% CI, minimum, P25, median, P75, and maximum at each assessment visit by treatment group. Graphical summaries will be provided using mean and 95% CI over time. This will also be summarized by prior ESA type, prior ESA dose, and ERI subgroup.

Number (%) of subjects by Hgb change from baseline category at Week 4 - daprodustat

The number and percentage of subjects within each category will be provided only for daprodustat group and the categories will be classified into 6 (i.e., ≤-2, >-2 to -1, >-1 to 0, >0 to 1, >1 to 2, >2 g/dL). In addition, ‘within ±1 g/dL (i.e., ≤-1 and ≥1)’ and ‘over ±2 g/dL (i.e., <-2 and >2)’ categories will be provided. This will also be summarized by prior ESA type, prior ESA dose, and ERI subgroup.

Number (%) of subjects with Hgb within the target range at each assessment visit

The number and percentage of subjects with Hgb within, above and below the target range will be summarized at each assessment visit by treatment group. Graphical summaries over time will also be produced.

Time (%) in the Hgb target range during the primary efficacy evaluation period

The time (weeks and percentage) within/above/below the target range will be summarized by treatment group using mean, standard deviation, minimum, P25, median, P75, and maximum. Treatment differences (daprodustat – darbepoetin alfa) and the associated 95% CIs for the time (weeks and percentage) within the target range will also be provided. See Section 15.6.3 for details.

Number (%) of subjects who have an Hgb level of less than 7.5 g/dL

The number and percentage of subjects who have an Hgb level of less than 7.5 g/dL during the treatment period will be summarized by treatment group. On-therapy Hgb values observed in both scheduled and unscheduled visits will be included in the summary.

Number (%) of subjects who have an Hgb increase of more than 2.0 g/dL over any 4 weeks

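### SAP 7.3.2 defines the supplementary Week 4 row for hemoglobin change within ±1 g/dL with its inequality signs reversed, so a count programmed from the bracket would be wrong

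*SAP*

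**What the plan says.** The objective is "To evaluate the appropriateness of the starting dose of daprodustat" (SAP 2.2; the same objective is in Protocol section 3). It has two endpoints. One is the Week 4 change from baseline in Hgb. The other is "Number (%) of subjects by Hgb change from baseline category at Week 4".

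For the second, SAP 7.3.2 sets six categories: "≤-2, >-2 to -1, >-1 to 0, >0 to 1, >1 to 2, >2 g/dL". The table "will be provided only for daprodustat group". The SAP then adds two further rows, each with its own inequality: "within ±1 g/dL (i.e., ≤-1 and ≥1" and "over ±2 g/dL (i.e., <-2 and >2". The table is repeated by prior ESA type, prior ESA dose and erythropoietin resistance index (ERI).

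Note [2] to the table in SAP 7.3.1 names the two extra rows by label only, with no inequality: "In addition, within ±1 g/dL and over ±2 g/dL".

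**The concern.** The first bracket contradicts its own label. A bracket introduced by i.e. is what a programmer codes and a checker checks against, and this one does not describe a change of at most 1 g/dL in either direction.

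The row bears on the argument for the starting dose. Protocol 4.5 supports 4 mg with simulations and clinical data suggesting that "Hgb levels observed with prior ESA therapy is maintained for 4 weeks after a switch from prior ESA to study medication", without a rapid rise above 2 g/dL. The share of subjects who stay within ±1 g/dL at Week 4 is a natural summary of the first part of that statement. A wrong count would misdescribe stability after the switch, overall and in every prior-ESA and ERI subgroup.

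**Working it through.** The plan states no count or percentage for this row, so there is no figure of its own to reproduce. The check is of the set logic, followed by an illustration of size.

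**Inputs.** The two brackets and the six categories come from SAP 7.3.2. The planned daprodustat group of 135 comes from Protocol 4.3. The mean and SD of the Week 4 change are not in the documents and are assumed. The worked example in SAP 15.6.3 shows Hgb to one decimal, so a 0.1 g/dL grid is used.

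**Step 1: the first bracket.** From -4.0 to +4.0 in steps of 0.1 there are 81 possible changes.

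- Both conditions together (at most -1 and at least 1): 0 values.
- Read as a union: -4.0 to -1.0 gives 31 values and +1.0 to +4.0 gives 31, in total 62.
- The interval that the label names, -1.0 to +1.0: 21 values.
- Overlap of the union with that interval: 62 + 21 - 81 = 2 values, exactly -1.0 and +1.0.

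Neither reading gives the band. The union is also the reading that the second bracket needs in order to contain anyone. A programmer who applies one convention to both rows therefore gets the outside of ±1 for the first.

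**Step 2: can the band be rebuilt from the six categories?** Each of the 81 values falls in exactly one category, so they are sound. The two middle categories hold -0.9 to 0.0 (10 values) and 0.1 to 1.0 (10 values), 20 in all. They miss only -1.0, which belongs to the category from above -2 up to -1.

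**Step 3: the second bracket.** Literally it holds 0 values. Read as both tails it holds 40 (-4.0 to -2.1 and 2.1 to 4.0), which is what its label says.

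**Step 4: size, if the first bracket were programmed as written.** Assume the change is Normal with mean 0. The intended share is 2Φ(1/SD) - 1, and the union share is one minus that.

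| Assumed SD (g/dL) | Intended | Both conditions | Union |
|---|---|---|---|
| 0.6 | 90.4% | 0% | 9.6% |
| 0.8 | 78.9% | 0% | 21.1% |
| 1.0 | 68.3% | 0% | 31.7% |

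With 135 subjects, the intended count runs from 0.904 × 135 = 122 down to 0.683 × 135 = 92. The union count runs from 0.096 × 135 = 13 up to 0.317 × 135 = 43.

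A wider set of assumptions takes mean m from -0.3 to +0.3 and SD from 0.6 to 1.2, with changes rounded to 0.1:

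- Intended, Φ((1.05 - m)/SD) - Φ((-1.05 - m)/SD): 60.4% to 92.0% (82 to 124 of 135).
- Union, Φ((-0.95 - m)/SD) + 1 - Φ((0.95 - m)/SD): 11.3% to 44.3% (15 to 60 of 135).
- Exactly -1.0, Φ((-0.95 - m)/SD) - Φ((-1.05 - m)/SD): 0.6% to 3.4% (about 1 to 5 of 135).

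**Step 5: is it put right elsewhere?** SAP 7.3.1 note [2] has the label only. SAP 15.6.3 gives no derivation for these rows. The revision history in SAP section 16 lists changes to 7.3 but not this one. The mock shells are separate documents (SAP 15.11) and were not available.

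**The case against.** The strongest reply is that this is a slip nobody would follow. The label appears twice, once without the faulty bracket, and leaves no doubt about what is meant. The row would be printed beside the two middle categories, which hold almost the same subjects, so a figure of 0% or of the complement would be conspicuous. The SAP says its display list was revised after a review of dry-run output, and the shell that governs the table may already be right. All of this stands. It makes the error likely to be caught, but it does not make the written rule correct.

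It is also fair to say that the second bracket is ordinary usage for two tails taken together. Changing its conjunction is a matter of clarity only.

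A reader might infer more than the documents support, in three ways:

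- **That the starting-dose endpoint is lost.** It is not. The SAP introduces the row as an addition. The six categories are exhaustive and correctly written, and the Week 4 change from baseline is specified separately in SAP 7.3.2 with full summary statistics.
- **That the trial's conclusions are at risk.** The table is descriptive, covers one arm and carries no test. Protocol 9.3.3 treats the other secondary endpoints as complementary or exploratory.
- **That the lowest category, at or below -2, must be made to match the second extra row.** The two serve different purposes. A strict bound is what over ±2 means, and forcing them to agree would spoil either the symmetric definition or a sound partition.

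**Conclusion.** The bracket is wrong as written and should be corrected. Taken literally it selects nobody. Taken as a union it selects changes at or beyond ±1 g/dL, which reverses the label except at exactly -1.0 and +1.0. Reversed signs are the evident cause. The non-strict signs in the bracket point to a closed band, from -1 to 1 inclusive.

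The consequence is confined to one supplementary row and its repeats by prior ESA type, prior ESA dose and ERI. The primary analysis, the principal secondary analysis and the type I error are untouched.

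The size (about 68% to 90% intended, against 0% or about 10% to 32%) rests on an assumed Normal change with mean 0 and SD 0.6 to 1.0 g/dL, and on the bracket being programmed literally. The documents give no basis for saying that it would be. This is a small correction to an operative definition, not a dispute about the choice of analysis.

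**What to change.** In SAP 7.3.2, define the first extra row as within ±1 g/dL (i.e., ≥-1 and ≤1). For clarity, define the second as over ±2 g/dL (i.e., <-2 or >2). Leave the six base categories unchanged. Add a footnote to the table and its subgroup repeats (SAP Tables 2.19 and 2.56) stating that a change of exactly -1.0 counts in the ±1 row although it falls in the category from above -2 up to -1. Check that the mock shell carries the same wording.

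The cost is one line of text and a footnote. No new data, analysis or change to the protocol is needed.

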### **7.3.3. Population of Interest**

The secondary efficacy analyses will be based on the ITT population, unless otherwise specified.

### **7.3.4. Strategy for Intercurrent (Post-Randomization) Events**

Any intercurrent events are taken to be irrelevant for secondary endpoints. The secondary endpoints will be summarized based on available and observed data.

### **7.3.5. Statistical Analyses / Methods**

Details of the planned displays are provided in [Appendix 10: List of Data Displays](#) and will be based on GSK data standards and statistical principles.

Unless otherwise specified, endpoints / variables defined in Section 7.3.1 will be summarized using descriptive statistics, graphically presented (where appropriate) and listed.

## 7.4. Exploratory Efficacy Analyses

### 7.4.1. Endpoint / Variables

[Endpoint / Parameter/ Display Type]	Absolute					
	Stats Analysis		Summary		Individual	
	T	F	T	F	F	L
Iron Use						
Dose of IV iron (mg) during the treatment period and the primary efficacy evaluation period (Week 40 to 52)			Y			
Dose of IV iron (mg) during the treatment period and the primary efficacy evaluation period (Week 40 to 52) by Baseline Iron Use			Y			
Number (%) of subjects who use iron during the treatment period and the primary efficacy evaluation period (Week 40 to 52)			Y			
Number (%) of subjects who use iron during the treatment period and the primary efficacy evaluation period (Week 40 to 52) by Baseline Iron Use			Y			
Iron Parameters (ferritin, TSAT, hepcidin, serum iron, and TIBC)						
Raw observed value at each assessment visit			Y	Y		Y
Raw observed value at each assessment visit by Baseline Iron Use			Y	Y		
Change from baseline at each assessment visit	Y	Y	Y			
Change from baseline at each assessment visit by Baseline Iron Use	Y	Y	Y			
Other						
Scatter plot of change from baseline in Hgb at Week 4 vs. covariates of interest – Daprodustat				Y		
Scatter plot of mean dose during Week 40 to 52 vs. covariates of interest – Daprodustat				Y		

#### NOTES :

- T = Table, F = Figure, L = Listing, Y = Yes display generated.
- Stats Analysis = Represents TFL related to any formal statistical analyses (i.e. modelling) conducted.
- Summary = Represents TFL related to any summaries (i.e. descriptive statistics) of the observed raw data.
- Individual = Represents FL related to any displays of individual subject observed raw data.

### 7.4.2. Summary Measure

- **Iron Use**

Dose of IV iron (mg) during the treatment period and the primary efficacy evaluation period

Monthly average IV iron dose by quarter (See Section 15.6.6) will be summarized using mean, standard deviation, minimum, P25, median, P75, and maximum. Quarter 1 (Day 1 to Week 12), Quarter 2 (Week 12 to Week 24), Quarter 3 (Week 24 to Week 40), Quarter 4 (Week 40 to Week 52), and whole treatment period will be used and the Quarter 4 represents the primary efficacy evaluation period. This will also be summarized by baseline iron use defined in Section 5.4.2.

Number (%) of subjects who use iron during the treatment period and the primary efficacy evaluation period

The number and percentage of subjects who use iron during the treatment period and the primary efficacy evaluation period will be summarized separately. These will also be summarized by baseline iron use defined in Section 5.4.2.

- **Iron Parameter (ferritin, TSAT, hepcidin, serum iron, and TIBC)**

Based on literature review the distributions of TSAT and hepcidin are skewed and require a log-transformation (See Section 5.2).

Raw observed value at each assessment visit

Ferritin, serum iron, and TIBC values will be summarized by treatment group using mean, standard deviation, 95% CI, minimum, P25, median, P75, and maximum at each assessment visit. TSAT and hepcidin values will be summarized by treatment group using geometric mean, standard error, coefficient of variation, and 95% CI based on log-transformed parameters, median, minimum, and maximum based on original scale at each assessment visit. These will also be summarized by baseline iron group. Graphical summaries will also be provided for each iron parameter.

Change from baseline at each assessment visit

Change from baseline in Ferritin, serum iron, and TIBC values will be summarized by treatment group using mean, standard deviation, 95% CI, minimum, P25, median, P75, and maximum at each assessment visit. Percent Change from baseline in TSAT and hepcidin values (Section 5.2) will be summarized by treatment group using geometric mean, coefficient of variation, and 95% CI based on log-transformed parameters, minimum, median, and maximum based on original scale at each assessment visit.

Treatment differences (daprodustat – darbepoetin alfa) and the associated 95% CIs for change from baseline will be provided at each assessment (See Section 7.4.5.1). For ferritin, serum iron, and TIBC change from baseline, graphical summaries will be provided by treatment group using the adjusted means and the associated 95% CIs over time. For TSAT and hepcidin percent change from baseline, graphical summaries will be provided using adjusted geometric means percent change from baseline and the associated 95% CIs over time. These will also be summarized by baseline iron group.

- **Other**

Scatter plot of change from baseline in Hgb at Week 4 vs. covariates of interest

Scatter plot of change from baseline in Hgb at Week 4 versus following covariates of interest, body weight, baseline Hgb, prior ESA dose will be produced only for daprodustat. See Section 15.6.3 for the detailed derivations.

Scatter plot of mean dose during Week 40 to 52 vs. covariates of interest

Scatter plot of mean dose during Week 40 to 52 versus following covariates of interest, body weight, baseline Hgb, prior ESA dose will be produced only for daprodustat. See Section 15.6.3 for the detailed derivations.

**7.4.3. Population of Interest**

The exploratory efficacy analyses will be based on the ITT population, unless otherwise specified.

**7.4.4. Strategy for Intercurrent (Post-Randomization) Events**

Any intercurrent events are taken to be irrelevant for exploratory endpoints and the exploratory endpoints will be summarized based on available and observed data.

Analysis of change from baseline in the respective iron parameter at each assessment visit will follow the strategy below.

Intercurrent events	Strategy
Study withdrawal / Intermittent missing	The following hypothetical scenario is considered to assess what would have happened if the event did not occur. Analysis using MMRM assume missing at random mechanism, that is the observations of missing depend on just observed values, not on unobserved values.

**7.4.5. Statistical Analyses / Methods**

Details of the planned displays are provided in Appendix 10: List of Data Displays and will be based on GSK data standards and statistical principles.

Unless otherwise specified, endpoints / variables presented in Section 7.4.1 will be summarized using descriptive statistics, graphically presented (where appropriate) and listed.

